- y) Obinutuzumab ADA and PK samples to be taken only in Cycle 5 and 7 before administration of RO7172508.
- z) sCEA to be assessed for enrollment in cohorts with RO7172508 doses < 12 mg.
- aa) PD blood flow cytometry to be taken from Cycle 5 onwards only at Cycles 8,12 and 16 at predose

Table 3 Part II: Multiple Participant Cohorts SC QW/Multiple Ascending Dose-Escalation

Cycle (21 days)	Screening ^x	Cycle 1								Cycle 2 - 4 ^a				Cycle 5 onwards ^a				End of Treatment	Safety Follow-Up	Survival Follow-Up ^r	Unscheduled (Safety)
Day	D-28 to D-1	Day 1	Day 2	Day 3	Day 5 ^t	Day 8	Day 10 ^o	Day 15	Day 17	Day 1	Day 5 ^f	Day 8	Day 15	Day 1	Day 5 ^z	Day 8	Day 15				
Assessments ^a		pre-dose	24 hrs post dose (±2 hrs)	48 hrs post dose (±4 hrs)	96 hrs post dose (±5 hrs)	pre-dose	48 hrs post dose (±4 hrs)	pre-dose	48 hrs post dose (±4 hrs)	pre-dose	96 hrs post dose (±1 day)	pre-dose	pre-dose	pre-dose	96 hrs post dose (±5 hrs)	pre-dose	pre-dose	incl. early discont. visit (e.g. progressive disease)	60 days after last treatment	90 Days after last treatment then every 3 mths ^r	e.g. In the event of an IRR ≥G2 ⁿ
Informed Consent ^b	X																				
Eligibility	X																				
Demography	X																				
Medical History	X																				
Pulmonary Function Tests ^w	X																				
Archival Tissue ^h	X																				
Previous and Concomitant Treatments		X																			
Adverse Events		X																			
Physical Examination	X	X								X				X				X	X		X
Anthropometric Measurements ^q	X	X								X				X					X		
Vital Signs ^v	X	X	X	X	X	X	X	X	X	X	X	X	X	X	X	X	X	X	X	X	X
ECOG Performance Status	X	X								X				X				X	X		X
ECG-12 lead ^d	X	X			X					X	X			X ^d				X	X		
Pregnancy Test ^e	X									X				X					X		

Table 3 Part II: Multiple Participant Cohorts SC QW/Multiple Ascending Dose-Escalation (cont.)

Cycle (21 days)	Screening ^z	Cycle 1								Cycle 2 - 4 ^a				Cycle 5 onwards ^a				End of Treatment	Safety Follow-Up	Survival Follow-Up ^r	Unscheduled (Safety)
Day	D-28 to D-1	Day 1	Day 2	Day 3	Day 5 ^t	Day 8	Day 10 ^o	Day 15	Day 17	Day 1	Day 5 ^r	Day 8	Day 15	Day 1	Day 5 ^{c,t}	Day 8	Day 15				

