Assessments ^a		pre-dose	24 hrs post dose (±2 hrs)	48 hrs post dose (±4 hrs)	96 hrs post dose (±5 hrs)	pre-dose	48 hrs post dose (±4 hrs)	pre-dose	48 hrs post dose (±4 hrs)	pre-dose	96 hrs post dose (±1 day)	pre-dose	pre-dose	pre-dose	96 hrs post dose (±5 hrs)	pre-dose	pre-dose	incl. early discontin. visit (e.g. progressive disease)	60 days after last treatment	90 Days after last treatment then every 3 mths ^r	e.g. In the event of an IRR ≥G2 ⁿ
Hematology ^f	X	X	X	X	X	X	X	X	X	X	X	X	X	X		X	X	X	X		
Blood Chemistry ^f	X	X	X	X	X	X	X	X	X	X	X	X	X	X		X	X	X	X		X
Coagulation ^f	X	X	X	X	X	X	X	X	X	X		X	X	X				X	X		X
Serology ^u	X																				
Urinalysis ^f	X	X								X				X				X	X		X
Fresh Tumor Biopsy ^g	X											X ^g						X ^g			
Tumor Assessment ⁱ	X									X ⁱ				X ⁱ				X			
Tumor Kinetics ^j	X																				
Administration of obinutuzumab ^x	X ^x																				
Obinutuzumab PK Sample ^{xy}	X ^x	x				x				x				X ^y				x			
ADA to obinutuzumab ^{xy}	X ^x													X ^y							
Administration of RO7172508 ^s		X ^s				X ^s		X ^s		X ^s		X ^s	X ^s	X ^s		X ^s	X ^s				
RO7172508 PK Sample		X	X	X	X	X	X	X	X	X	X	X	X	X	X	X	X	X	X		X
ADA to RO7172508		X				X		X		X		X	X	X				X	X		X
sCEA	x ^z	X	X	X	X	X	X	X	X	X	X	X	X	X				X	X		X
PD Blood Flow Cytometry		X	x			X	x			X		X		x ^{aa}				x			
PD Blood Cytokines		X	X	X	X	X	X	X	X	X	X	X	X ^p	X ^k	X ^k			X			X ⁿ
TCR Vβ ^l		X												X ^l							
CtDNA/tumor markers		X												X ^m							

Table 3 Part II: Multiple Participant Cohorts SC QW/Multiple Ascending Dose-Escalation (cont.)

Cycle (21 days)	Screening ^x	Cycle 1								Cycle 2 - 4 ^a				Cycle 5 onwards ^a				End of Treatment	Safety Follow-Up	Survival Follow-Up ^r	Unscheduled (Safety)
Day	D-28 to D-1	Day 1	Day 2	Day 3	Day 5 ^t	Day 8	Day 10 ^o	Day 15	Day 17	Day 1	Day 5 ^t	Day 8	Day 15	Day 1	Day 5 ^t	Day 8	Day 15				
Assessments ^a		pre-dose	24 hrs post dose (±2 hrs)	48 hrs post dose (±4 hrs)	96 hrs post dose (±5 hrs)	pre-dose	48 hrs post dose (±4 hrs)	pre-dose	48 hrs post dose (±4 hrs)	pre-dose	96 hrs post dose (±1 day)	pre-dose	pre-dose	pre-dose	96 hrs post dose (±5 hrs)	pre-dose	pre-dose	incl. early discontin. visit (e.g. progressive disease)	60 days after last treatment	90 Days after last treatment then every 3 mths ^r	e.g. In the event of an IRR ≥G2 ⁿ
Clinical Genotyping		X																			
RBR Sample (DNA)		X																			
RBR Sample (RNA)		X												X ^m							
IgE and Tryptase																					X ⁿ

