Notes: ADA=anti-drug antibody; AE=adverse event; C=Cycle; CEA=carcinoembryonic antigen; ct=circulating tumor; D=day; discontin=discontinuation; DNA=deoxyribonucleic acid; ECG=electrocardiogram; ECOG=Eastern Cooperative Oncology Group; G2=grade 2; HIV=human immunodeficiency virus; IgE=immunoglobulin E; incl=including; IRR=infusion related reaction; PD=pharmacodynamics; PK=pharmacokinetic; RBR=Research Biosample Repository; RECIST=Response Evaluation Criteria in Solid Tumors; RNA=ribonucleic acid; sCEA=soluble CEA; TCR=T cell receptor.

- a) All visits from Cycle 3 onwards should occur within a 3-day time window, unless otherwise indicated and all assessments or samples where indicated should be taken prior to the administration of RO7172508.
- b) Informed consent must be obtained before any study-specific procedures *and may be obtained > 28 days before the start of study treatment.*
- c) Day 5 visit to be done only every second cycle after Cycle 5. (i.e. C7, C9 etc.).
- d) 12-lead ECG at screening (within one week before first dose of RO7172508). After Cycle 4, 12-lead ECG to be done only at every second cycle (i.e. Cycle 6, Cycle 8 etc.). Additional unscheduled ECG assessments in triplicate should be performed in case of abnormalities and if clinical symptoms occur. Recording must be done prior to PK sampling.
- e) Serum pregnancy test at screening, within 7 days prior to first dose, and at the safety follow-up visit; a urine pregnancy test will be performed at specified subsequent visits. If a urine pregnancy test is positive, it must be confirmed by a blood pregnancy test. Results must be obtained and reviewed prior to administration of RO7172508.

Table 3 Part II: Multiple Participant Cohorts QW SC/Multiple Ascending Dose-Escalation (cont.)

- f) Hematology, blood chemistry, coagulation, and urinalysis can be performed within 24 hours (up to 72 hours if during weekend) prior to scheduled dosing. Screening results can be within 1 week prior to C1D1. Results must be obtained and reviewed prior to administration of RO7172508.
- g) Tumor biopsy samples will be collected during screening, once during the study treatment period at Cycle 2 Day 8 and optionally at the end of treatment visit ONLY if the reason for discontinuation is progressive disease. If a fresh biopsy is performed for screening purposes, this can be used as the baseline sample.

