- h) As part of the eligibility procedure, CEA expression will be confirmed on archival tumor material, *with the exception of CRC participants*. If no archival tumor sample is available, fresh sample will be collected and be assessed (the same sample would constitute as baseline screening sample if participant is enrolled). Archival tissue should be submitted for additional biomarker assessments for all participants (if available).
- i) Tumor response is assessed by the Investigator per RECIST V1.1 with the use of physical examination and image-based evaluation. All measurable and evaluable lesions should be assessed and documented during the screening period, within 7 days before Cycle 3 Day 1, thereafter every 6 weeks (\pm 7 days) for 12 weeks, and then every 12 weeks (\pm 7 days) until disease progression or death. (i.e. screening, C3, C5, C7, C11, C15, C19 etc.).
- j) To allow estimation of tumor growth rate before start of treatment, an exploratory assessment of tumor kinetics will be made by comparing post treatment scans with at least 2 pretreatment scans not older than 12 weeks prior to C1D1, if available. One of the pretreatment scans will be the study baseline scan taken during screening and the second will be within the preceding 12 weeks.
- k) Cytokines from Cycle 5 onwards, samples to be taken every second cycle up to Cycle 15 (e.g. C5, C7 etc.).
- l) TCR V β samples to be drawn at Cycle 1 Day 1 predose (baseline) and Cycle 5 Day 1 predose.
- m) RBR (RNA) and CtDNA/tumor markers samples to be taken on Cycle 5 only.
- n) Sample to be taken only if a \geq Grade 2 safety event is suspected to be immune-related (e.g., IRR). Refer to [Table 5](#) for additional assessments if safety event is an IRR/CRS (\geq Grade 3) that requires tocilizumab treatment. *Any biopsy samples or results done as part of standard of care can be shared with the Sponsor if applicable.*
- o) Visit may be omitted depending on emerging safety data for SC and/or fractionated dosing regimens after discussion between Investigators and the Sponsor.
- p) Cytokines sample to be taken on Cycle 2 only.
- q) Weight to be recorded pre-infusion. Height to be measured at screening only.
- r) Survival follow-up visit to be performed 90 days (\pm 7 Days) after the last treatment either in person or a phone call to document any ongoing or resolved AEs, and every 3 months (\pm 2 weeks) thereafter for overall survival.

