- s) All planned assessments are to be performed before administration of RO7172508.
- t) Day 5 visit optional if it falls on a non-working day *and can be performed +/- 1 day.*
- u) Serology (as per local regulations) includes HIV, hepatitis B surface antigen, total hepatitis B core antibody, hepatitis C virus antibody. Results must be obtained and reviewed prior to administration of RO7172508.
- v) Vital signs include systolic and diastolic blood pressure; pulse rate; temperature; respiratory rate and oxygen saturation.

Table 3 Part II: Multiple Participant Cohorts QW SC/Multiple Ascending Dose-Escalation (cont.)

- w) Pulmonary function tests should include spirometry; forced expiratory volume (FEV1), forced vital capacity (FVC) and Diffusion capacity (DLCO).
- x) Refer to [Table 6](#) in the event obinutuzumab pre-treatment is implemented for specific additional assessments during the screening period.
- y) Obinutuzumab ADA and PK samples to be taken only in Cycle 5 and 7 before administration of RO7172508.
- z) sCEA to be assessed for enrollment in cohorts with RO7172508 doses < 12 mg.
- aa) PD blood flow cytometry to be taken from Cycle 5 onwards only at Cycles 8,12 and 16 at predose

Table 4 Part II: Fractionated Dosing IV Cohort for Q3W

Cycle (21 days)	Screening ^v	Cycle 1											Cycle 2 - 4 ^a				Cycle 5 onwards ^a			End of Treatment	Safety Follow-Up	Survival Follow-Up ^r	Un-scheduled (Safety)			
Day	D-28 to D-1	Day 1		Day 2	Day 3	Day 8	Day 9 ^p	Day 15	Day 16 ^p	Day 1	Day 3	Day 8	Day 15	Day 1	Day 3 ^c	Day 15										
Assessments ^a		pre-dose	EOI +15 mins	2 hrs EOI ±15 mins	24 hrs EOI ±2 hrs	48 hrs EOI ±4 hrs	pre-dose	EOI +15 mins	24 hrs EOI ±2 hrs	pre-dose	EOI +15 mins	24 hrs EOI ±2 hrs	pre-dose	EOI +15 mins	2 hrs EOI ±15 mins	48 hrs EOI ±4 hrs			pre-dose	EOI +15 mins	48 hrs EOI ±4 hrs	incl. early discontin. visit (e.g. progressive disease)	60 Days after last treatment (±5 Days)	90 Days after last treatment then every 3 mths ^r	e.g. In the event of an IRR ≥G2 ^o	
Informed Consent ^b	X																									
Eligibility	X																									
Demography	X																									
Medical History	X																									
Pulmonary Function Tests ^v	X																									
Archival Tissue ^h	X																									
Previous and Concomitant Treatments		X																								
Adverse Events		X																								
Physical Examination	X	X											X						X				X	X		X

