9.4 STATISTICAL ANALYSES

The data will be analyzed by the Sponsor and/or designated Contract Research Organization (CRO). Any data analysis carried out independently by the Investigator should be submitted to the Sponsor before publication or presentation. The data will be summarized with respect to demographic and baseline characteristics, efficacy observations and measurements, safety observations and measurements, pharmacokinetic and biomarker measurements. Data will be summarized by cohort and regimen within each part and CEA level where applicable, *including the additional participants that may be enrolled in expanded cohorts (see Section 4.1.2.2)*. *Participants who receive only obinutuzumab but no dose of RO7172508 will be summarized separately.*

The baseline value of any variable will be defined as the last available value prior to the first administration of study treatment (RO7172508 or obinutuzumab (if applicable) as appropriate).

The following endpoints may be used to select a route of administration for further development: PD parameters including T-cell activation in blood and in the tumor; pharmacokinetic parameters such as AUC, C_{max} and half-life; tolerability and safety; as well as incidence of ADAs and their effect on exposure. Clinical efficacy will be considered, but is not expected to be a key criterion, as efficacy will likely be affected by parameters which cannot be controlled for in such small cohorts. Data will be listed and summarized by dose group as described in this analysis section. Analyses are exploratory in nature and no formal hypothesis testing will be performed.

If one route of administration is not unequivocally superior, and a decision cannot be taken during or at the end of dose escalation, both routes of administration will be compared in disease specific expansion. Criteria for selection of a route of administration will then be added via the amendment preceding the expansions, including endpoints.

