9.4.4 Pharmacokinetic Analyses

PK parameters will be read directly from the serum concentration-time profiles or calculated by using standard non-compartmental methods. Estimates for PK parameters,

including C_{max} , AUC, $t_{1/2}$, minimum drug concentration (C_{min}), *clearance* (CL) and volume of distribution at steady state (V_{ss}) will be tabulated and summarized.

Analyses will be carried out on the PK analysis population. All PK parameters will be presented by listings and descriptive summary statistics (mean, standard deviation, coefficient of variation, median, minimum, and maximum) separately by group or cohorts.

Individual and mean serum RO7172508 concentration versus time data will be tabulated and plotted by dose-level. Graphical displays of PK data may also be provided.

Monitoring and characterization of ADA responses and their potential impact on PK will also be investigated.

In addition, data may be analyzed using population PK modeling; results will be reported separately.

Individual and mean serum obinutuzumab concentration versus time data will be tabulated.

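### Weekly SC schedule: the Day 5 visit may be skipped on non-working days, leaving only trough PK samples in Cycles 2-4, although the existing ±1 day window makes skipping unnecessary on ordinary weekends

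*Combined protocol and SAP*

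**What the plan says.** Section 1.3, Table 3 sets out the weekly SC schedule. Footnote t makes the "Day 5 visit optional if it falls on a non-working day" and continues "and can be performed +/- 1 day". It names no cycle.

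- **PK, Cycle 1:** Days 1, 2, 3, 5, 8, 10, 15 and 17. Days 1, 8 and 15 are pre-dose. Day 10 has its own footnote: "Visit may be omitted depending on emerging safety data for SC and/or fractionated dosing regimens after discussion between Investigators and the Sponsor". Day 17 carries no such note.
- **PK, Cycles 2-4:** Days 1, 8 and 15, all pre-dose, and Day 5, headed "96 hrs post dose (±1 day").
- **PK, Cycle 5 onwards:** the same four days, but the Day 5 visit takes place only in every second cycle (footnote c).
- **ECG:** Day 1 pre-dose and Day 5 in Cycles 1-4. Footnote d then says: "After Cycle 4, 12-lead ECG to be done only at every second cycle", and that ECG is on Day 1 pre-dose. Further ECGs are scheduled at screening, end of treatment and safety follow-up.

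The Day 5 column heading allows ±5 h in Cycle 1 and from Cycle 5 on, but ±1 day in Cycles 2-4.

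Section 9.4.4 states how Cmax is obtained: "PK parameters will be read directly from the serum concentration-time profiles or calculated by using standard non-compartmental methods". Section 9.4 lists "pharmacokinetic parameters such as AUC", Cmax and half-life among the endpoints that may guide the choice of route. Section 4.1.3 defines loss of exposure as a fall in Cmax of at least 70% from Cycle 1 to Cycle 3.

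**The concern.** In Cycles 2-4, removing Day 5 leaves three samples, each drawn just before an injection. A Cmax read from that profile is the highest trough. It cannot exceed the value obtained with Day 5 and will usually be lower.

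The loss would not be random. Cycles last 21 days, so a participant whose Day 5 falls on a weekend in one cycle meets the same conflict in every cycle unless the dosing day moves.

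Two uses of Cmax are exposed. In the loss-of-exposure rule, a skipped Cycle 3 visit lowers the numerator while Cycle 1 keeps its 24 h and 48 h samples, so the error points towards declaring a loss. In the comparison of routes, later-cycle SC Cmax would be set against IV cycles that include end-of-infusion samples (Table 2). The skipped visit also removes that cycle's only ECG between doses.

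**Working it through.** **1. Which samples remain.** Reading across the 21 columns of Table 3, the PK and ECG rows align with the headings as listed above. Without Day 5, Cycles 2-4 keep only the pre-dose draws of Days 1, 8 and 15, and the ECG row keeps only Day 1 pre-dose. The superscripts on the Day 5 headings vary from page to page in the text available for this check; footnote t is read as applying to Day 5 in every cycle, as its wording suggests.

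**2. Is skipping needed?** Day 5 is Day 1 plus 4 calendar days.

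| Dosing day | Day 4 | Day 5 | Day 6 | Working day within ±1 day |
|---|---|---|---|---|
| Monday | Thu | Fri | Sat | Day 5 itself |
| Tuesday | Fri | Sat | Sun | Day 4 (Friday) |
| Wednesday | Sat | Sun | Mon | Day 6 (Monday) |
| Thursday | Sun | Mon | Tue | Day 5 itself |
| Friday | Mon | Tue | Wed | Day 5 itself |

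Two of the five weekdays put Day 5 on a weekend, and the window recovers both. A closure of three or more days can defeat it, for example a Tuesday start followed by a Friday holiday.

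**3. Size of the effect.** The plan states no figure to reproduce and gives no SC absorption rate or half-life, so the inputs here are assumptions. Take one compartment with first-order absorption, weekly doses at days 0, 7, 14 and so on, and dose × bioavailability / volume set to 1:

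C(t) = Σ ka/(ka − ke) × [exp(−ke·u) − exp(−ka·u)], with u = time since each dose and ke = ln 2 / half-life.

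Cycle 3 Day 1 is t = 42. The samples are at t = 42, 46 (Day 5), 49 and 56; the true peak is the maximum over t = 42 to 63.

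Example with ka = 0.5 per day and half-life 5 days, so ke = 0.693/5 = 0.139 per day: C(42) = 0.799, C(46) = 1.085, C(49) = 0.800, C(56) = 0.801, true peak 1.168.

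- Day 5 attended: 1.085/1.168 = 93%.
- Day 5 skipped: 0.801/1.168 = 69%.
- Moved to Day 4: C(45) = 1.150, and 1.150/1.168 = 98%.
- Moved to Day 6: C(47) = 0.996, and 0.996/1.168 = 85%.

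Over 15 pairs (ka 0.3, 0.5, 0.8 per day; half-life 3, 5, 7, 10, 14 days), observed Cycle 3 Cmax as a share of the true peak:

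| Day 5 | Range |
|---|---|
| Attended at 96 h | 78-97% |
| Skipped | 42-90% |
| Moved to Day 4 | 91-100% |
| Moved to Day 6 | 64-94% |

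Moving the visit gives a higher value than skipping it in all 15 pairs.

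**4. Cycle 1.** The overall observed Cmax is identical with and without Day 5 in all 15 pairs, because the 48 h samples after later doses remain. Within the first dosing interval alone it is 95-100% of the true maximum with Day 5 and 85-100% without.

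**5. Loss-of-exposure rule.** The rule is met when Cycle 3 Cmax / Cycle 1 Cmax is at most 0.30. On a wider grid of 25 combinations (ka 0.1-1.0 per day, half-life 1-14 days), with no true loss, skipping Day 5 in Cycle 3 alone brings the ratio below 0.30 in 3 cases (0.05, 0.18 and 0.23), all with half-life 1-2 days and ka 0.5-1.0 per day. With Day 5 attended the lowest ratio is 0.34.

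**The case against.** **The effect is confined to later cycles.** This stands. A reader might infer that SC Cmax as a whole is biased low, or that the SC rationale in Section 4.1 is undermined. The documents do not support either: Section 4.1 speaks of a lower Cmax after the first administration, where the 24 h and 48 h samples also exist.

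**The magnitude is assumed.** This stands too. On the wider grid, observed Cycle 3 Cmax is only 33-98% of the true peak even when Day 5 is attended, so part of any shortfall comes from having one sample between doses, not from the footnote. No effect on AUC has been calculated.

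**How many participants would be affected is unknown.** One might turn two weekdays out of five into 40% of participants. That needs dosing spread evenly over the week, which the documents do not state; the timed Day 2 and Day 3 visits in Cycle 1 discourage late-week starts. It would also count those who may skip, not those who do.

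**Other ECGs exist.** It would be wrong to call Day 5 the only post-dose ECG: there are ECGs at end of treatment and safety follow-up, and unscheduled triplicate ECGs for abnormalities or symptoms. The point holds only for ECGs within a dosing interval.

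**The plan has safeguards.** Sampling times may be changed on emerging data (Section 8.5), incomplete profiles may be excluded (Section 9.3) and population PK modelling is allowed (Section 9.4.4). These limit the bias, but exclusion replaces it with missing data.

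**Table 7 is not an exact parallel.** Its Day 5 visit occurs in Cycles 1-2 only and carries no ECG. It shows only that the other SC schedule uses a ±1 day window without permission to skip.

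**Conclusion.** The point holds as a minor, nearly cost-free design correction. Footnote t permits a visit to be dropped that is the only non-trough PK sample of Cycles 2-4 and the only ECG within a dosing interval in Cycles 1-4, while the same sentence supplies a window that covers every ordinary weekend. Where the visit is dropped, Cmax for that cycle is biased low, or missing if the profile is excluded; the same applies to later cycles that have a Day 5 visit.

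The size, 42-90% of the true Cycle 3 peak against 78-97%, rests on the assumed one-compartment model and parameter range, not on trial data. A reader might infer that skipped visits would often produce false loss-of-exposure calls. That is not supported: on the skip alone it needed a half-life of 1-2 days, and the plan describes the half-life as prolonged relative to cibisatamab, without giving a value. Effects on route selection are also limited, since Cmax is one of several endpoints that may be considered and no formal testing is planned.

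**What to change.** Reword Table 3 footnote t along these lines: 'If Day 5 falls on a non-working day, the visit is moved by 1 day (Day 4 or Day 6); it is omitted only if no working day falls within this window.' The last clause keeps long holiday closures from becoming protocol deviations.

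In the same edit, reconcile the ±5 h Day 5 headings in Cycle 1 and from Cycle 5 on with the ±1 day window.

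The cost is one footnote, two column headings and slightly less flexibility for sites. The visit, PK sample and ECG are already scheduled, and Section 8.5 already requires the date and time of each sample to be recorded, so a moved sample can be analysed at its actual time.
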